## **17.2 Steps to secure the data during storage, use, and transmission**

Participants' identifying information will be kept separate from their demographic questionnaire and their other surveys for this study within REDCap. Participants' responses and objective data will be linked to identifying information only through a unique identifier and the information used to link records with identifying information will be kept in a securely locked file cabinet only accessible to the study team. Electronic data will be stored in password protected databases on the secure Hackensack Meridian Health server. Identifying information will not be included on datasets used for statistical analysis and study progress reports.

## **17.3 Information included in that data or associated with the specimens**

No specimens will be stored as part of this study. The only specimens collected will be the two spot blood samples which will be sent to OmegaQuant lab. The data will include variables describing participants' survey responses, and any notes in REDCap from 12 weekly check-in calls from the RC.

For the two spot blood sample tests for each subject, the specimens will be coded before being sent to OmegaQuant Lab, associated with University of South Dakota Medical Center. This lab will only receive de-identified samples, and no identifying patient information.

- *Mode of data storage.*  
Data collected from questionnaires will be stored on the REDCap database on the HMH server. Any paper files will be stored on site at HUMC in locked file cabinets only accessible by the study staff.
- *Duration of data storage.*  
Data will be stored for 6 years after the end of the study, per HMH requirements.
- *Access to data.*  
Access to the data will be restricted to the study staff.
- *Responsibility for receipt or transmission of the data.*  
The PI will be responsible for receipt and transmission of the data.
- *Transportation of the data.*  
The data should not need to be transported. However, if there is a need to transport the data, secure file transfer will be used.
- *Type of data being collected, stored, transmitted and shared.*
  - Protected Health Information (PHI)

- Personally Identifiable Information (PII)
- All computer software to protect against malware will be kept up-to-date and operational. All operating system and software updates and patches will be applied regularly.
- Codes linking participants' identifying information with de-identified data will be stored separately from the corresponding data sets.
- The data will only be accessed on HMH workstations and laptops such that encryption and password protection will be in place with two-factor authentication required for access.
- Access to the data is limited to the study team. Any study staff added to the project will be approved by the PI and added to the IRB protocol.

All HMH policies and procedures for data collection, storage, transmission and destruction will be followed.

## 18.0 Informed Consent Process

*Obtaining consent:*

- The consent process will take place online via REDCap.
- No waiting period is required between informing prospective participants and obtaining consent.
- The study will follow the informed consent process for research.

Process to Document Consent in Writing

- The study will document participants' informed consent in writing (electronically) via REDCap.
- The consent document will be attached to the IRB submission.

## 19.0 Adverse Event Reporting and Monitoring

Clinical criteria for withdrawing an individual subject: Subjects may call the PI at the phone number listed on the consent form at any time to report any concerns which may or may not warrant withdrawal from the study. Additionally, the subject will receive a check-in call 1x per week to discuss any issues of concern. The study physicians, [name] and [name], will be informed of any issues that arise which may or may not warrant a subject being removed from the study due to safety or toxicity concerns.

### 19.1 Adverse Events

#### 19.1.1 Definitions

**Unanticipated problems involving risk to participants or others:** Any incident, experience, outcome, or new information that:

1. Is unexpected; and
2. Is related or possibly related to participation in the research; and
3. Indicates that subjects or others are at a greater risk of harm (including physical, psychological, economic, legal or social harm) than was previously known or recognized.

**Unexpected.** The incident, experience or outcome is not expected (in terms of nature, severity, or frequency) given the research procedures that are described in the study related documents, such as the IRB-approved research protocol/research plan and informed consent documents; and the characteristics of the subject population being studied.

**Related.** There is a reasonable possibility that the incident, experience, or outcome may have been caused by the procedures involved in the research.

**Adverse event (AE):** Any untoward medical occurrence in a patient or clinical investigation subject administered a pharmaceutical product and which does not necessarily have to have a causal relationship with this treatment. An AE can therefore be any unfavorable and unintended sign (including an abnormal laboratory finding, for example), symptom, or disease temporally associated with the use of study treatment, whether or not considered related to the study treatment.

**Serious adverse event (SAE):** Any untoward medical occurrence that, at any dose, results in death; is life threatening (i.e., an event in which the patient was at risk of death at the time of the event; it does not refer to an event that hypothetically might have caused death if it were more severe); requires inpatient hospitalization or prolongation of existing hospitalization; results in persistent or significant disability/incapacity; or is a congenital anomaly/birth defect.

### **19.1.2 Reporting of AEs/SAEs**

AE will be reported and recorded from the time of the first dose of study drug through 30 days after the last dose of study drug. AE monitoring should be continued for at least 30 days following the last dose of study supplement. AEs (including laboratory abnormalities that constitute AEs) should be described using a diagnosis whenever possible, rather than individual underlying signs and symptoms. When a clear diagnosis cannot be identified, each sign or symptom should be recorded as a separate AE. The Investigator should ask the patient non-leading questions to determine if any AEs have occurred during the study, since the last visit. AEs may also be recorded when they are volunteered by the patient, or through physical examination, laboratory tests, or other clinical assessments. An AE should be followed and an assessment should be made at each visit (or more frequently, if necessary) of any changes in severity of the event, the suspected relationship to the study treatment, the interventions required to treat the event, and the outcome.

It is the responsibility of the PI (and/or sub-investigators) to report all unanticipated problems involving risks to subjects or others to HMH IRB.

For unanticipated problems/adverse events associated with clinical trials that do not meet the criteria in Section 19.1.1, the investigator or study team member should describe the events at the time of continuing review.

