Long-term effects of covid-19 include loss of taste, loss of smell, continued need for oxygen therapy, and more. One New Jersey-based study on 183 patients from Hackensack University Medical Center found that at 35 days after discharge from the hospital following treatment for covid-19, 55% reported fatigue, 45.3% dyspnea, and 51% muscular pain, among other symptoms [8]. For some, post-covid syndrome lasts several weeks, while for others it may last several months. A small number of patients are thought to perhaps never return back to their pre-covid baseline.

According to the Mayo Clinic [7], the most common signs and symptoms of long covid syndrome are:

- Fatigue
- Shortness of breath
- Cough
- Joint pain
- Chest pain

Mayo Clinic states other long-term signs and symptoms may include: [7]

- Muscle pain or headache
- Fast or pounding heartbeat
- Loss of smell or taste
- Memory, concentration or sleep problems
- Rash or hair loss
- Organ damage, in particular:
  - “Heart. Imaging tests taken months after recovery from COVID-19 have shown lasting damage to the heart muscle, even in people who experienced only mild COVID-19 symptoms. This may increase the risk of heart failure or other heart complications in the future.
  - Lungs. The type of pneumonia often associated with COVID-19 can cause long-standing damage to the tiny air sacs (alveoli) in the lungs. The resulting scar tissue can lead to long-term breathing problems.
  - Brain. Even in young people, COVID-19 can cause strokes, seizures and Guillain-Barre syndrome — a condition that causes temporary paralysis. COVID-19 may also increase the risk of developing Parkinson's disease and Alzheimer's disease.” [7]
- Blood clots and blood vessel issues
  - “COVID-19 can make blood cells more likely to clump up and form clots. While large clots can cause heart attacks and strokes, much of the heart damage caused by COVID-19 is believed to stem from very small clots that block tiny blood vessels (capillaries) in the heart muscle.
  - Other parts of the body affected by blood clots include the lungs, legs, liver and kidneys. COVID-19 can also weaken blood vessels and cause

them to leak, which contributes to potentially long-lasting problems with the liver and kidneys.” [7]

- Mood and fatigue issues

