## Inclusion/Exclusion Eligibility Survey

Please complete the survey below.

Thank you!

---

1. Are you a team member at Hackensack Meridian Health?  Yes  No

---

2. Are you age 18 or over?  Yes  No

---

3. Have you tested positive for coronavirus (COVID-19) via PCR test? (Note: home test or other rapid test MUST be confirmed by a PCR test)  Yes  No

---

4. On what date were you diagnosed with Covid-19 via PCR test? \_\_\_\_\_

---

5. Have you been experiencing symptom(s) related to covid-19 for more than 12 weeks after initial infection?  Yes  No

---

6. Which of the ongoing covid-19 symptoms have you been experiencing? (please check all that apply)  Respiratory symptoms (shortness of breath and/or cough)  Fatigue  Loss of taste  Loss of smell

---

7. Were any of these symptoms present before your covid-19 infection?  Yes  No

---

8. Where you ever hospitalized for covid-19?  Yes  No

---

9. Did you require supplemental oxygen for covid-19?  Yes  No

---

10. Do you have a known soy allergy?  Yes  No

---

11. Do you have a known allergy to fish?  Yes  No

---

12. Are you able to take an online survey every other week (bi-weekly) for the study?  Yes  No

---

13. Are you able to take your own blood pressure and record it in bi-weekly online survey?  Yes  No

---

14. If you qualify, are you willing to participate in this 12-week study and be assigned to either intervention or placebo arm? This means you will be assigned to either take the omega-3 supplement or a placebo (pill with soybean oil in it).  Yes  No

Confidential

Confidential

Page 2

15. Are you currently taking an omega-3 supplement or other high-dose supplement (over 2,000 IU) with potential for aiding recovery of long covid syndrome (e.g. zinc, Vit C, Elderberry)?

 Yes No

16. Are you able to take/swallow six mini-pills daily?

 Yes No I don't know

17. Are you able and willing to give a spot blood sample (2 drops) at the beginning (baseline) and end of the study?

 Yes No

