## Demographic / Baseline Survey - Covid Recovery Study

Page 1

Please complete the survey below.

Thank you!

What is your last name?

---

Please provide your mailing address so that we can mail your kit of supplies for study participation.  
Your supplies will arrive by FedEx, in 2 shipments.

---

What is your first name?

---

What is your gender?

- Female
- Male
- Unknown

What is your race?

- Black or African American
- White
- Asian
- American Indian or Alaska Native
- Other
- Unknown

(choose multiple if needed)

What is your ethnicity?

- Hispanic
- Non-Hispanic
- Unknown

Other race not listed above

---

What is your cell phone number? (This will only be used by the study team to reach you.)

---

What is your work phone number? (This will only be used by the study team to reach you.)

---

What is your age?

---

Has any doctor or other health care provider ever told you that you have any of the following illnesses?  
(please check all that apply)

- Diabetes or high blood sugar
- Hypertension or high blood pressure
- High cholesterol
- Stroke (ischemic or hemorrhage)
- Chronic lung disease such as asthma, emphysema, or chronic bronchitis
- Heart disease
- Cancer (other than skin cancer)
- Depression
- HIV/AIDS
- COPD
- Other

If "other" is checked off, please specify.

---

Confidential

Page 2

Please list any recent (adult) allergies to food, medicine, herbal or environmental items, with the reactions and dates.

---

Do you use tobacco products ( e.g., cigarettes, cigarillos, e-cigs, cigars)?

- Yes, I currently use tobacco products
- No, but I used tobacco products in the past
- No, I have never used tobacco products

---

Have you received the covid-19 vaccine?

- Yes
- No

---

Are you currently experiencing any side effect(s) from the covid-19 vaccine?

- Yes
- No

---

If yes, please describe:

---

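### Adverse events count from the first capsule, but no form is stated to record beforehand which other symptoms a subject has, or how severe any are, so old long-covid complaints may be logged as on-treatment events

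*Combined protocol and SAP*

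**What the plan says.** **Window and definition.** Section 19.1.2: "AE will be reported and recorded from the time of the first dose of study drug", continuing to 30 days after the last dose. Section 19.1.1 includes any unfavorable sign, "symptom, or disease temporally associated with the use of study treatment, whether or not considered related to the study treatment". Where there is no clear diagnosis, "each sign or symptom should be recorded as a separate AE". The items to be followed for each event are change in severity, suspected relationship, interventions and outcome. Onset and presence before dosing are not among them, and neither section limits events to symptoms that are new or worse.

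**How events are elicited.** Section 19.1.2: "The Investigator should ask the patient non-leading questions to determine if any AEs have occurred during the study, since the last visit".

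**What is recorded before dosing.**
- Appendix A, item 6: "Which of the ongoing covid-19 symptoms have you been experiencing", with boxes for respiratory symptoms, fatigue, loss of taste and loss of smell. It has no severity scale and no box for anything else.
- Appendix B: "Has any doctor or other health care provider ever told you that you have any of the following illnesses", with a free-text other illness; allergies with their reactions; tobacco use; and "Are you currently experiencing any side effect(s) from the covid-19 vaccine". It has no symptom list.

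**What comes later.** Appendix C is sent every two weeks during the 12 weeks (Section 1.0). It has a row for other symptoms, with room to describe three. It asks when a symptom stopped, counted from the covid diagnosis, and not when it began.

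**What subjects may already have.** Section 3.0 lists persistent complaints well beyond the four targets, among them joint pain, chest pain, headache and "Memory, concentration or sleep problems".

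**The concern.** Section 10.0 admits only people with at least one ongoing target symptom, so the whole sample is symptomatic at entry, and many may have other long-covid complaints. If such a complaint is first mentioned on a weekly call after dosing starts, nothing in the stated pre-dose record shows that it is old. For the four target symptoms, presence is known but grade is not, so worsening cannot be judged either.

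The event label has consequences. Section 17.1 summarizes all data by arm. Section 15.0 has the investigator decide on continued participation after an event, and sets a study-stopping rule on events in the first 10 subjects with no new-onset requirement. Section 8.0 unblinds a subject who drops out because of an event. Section 19.2 has the DSMB review the trial monthly. Baseline status cannot be reliably reconstructed once dosing has begun.

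**Working it through.** **Plan's own figure.** There is none to reproduce. The documents give 50 per arm with no event rate, effect size or power, and Section 17.1 says the study is not powered for analyses.

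**Step 1: can old be told from new on the stated forms?**

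| Symptom type | Presence before dosing | Severity before dosing | Onset asked later |
|---|---|---|---|
| Four target symptoms | Yes (Appendix A) | No | No |
| Vaccine side effects | Yes (Appendix B) | Free text only | No |
| Other long-covid complaints | No, unless given as a diagnosed illness | No | No |
| Side effects named in Section 15.0 | No, unless given as a diagnosed illness | No | No |

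In Appendix C, an old symptom and a new one that are both continuing receive the same answer. Appendix C does grade fatigue, but no completion before dosing is stated.

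**Step 2: effect on a pooled any-event comparison.** Let p be the true on-treatment event proportion in an arm. Let B be the share of each arm with a pre-existing complaint logged as an event, taken as equal in the two arms and independent of true events. Then:

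- observed proportion q = 1 − (1 − B)(1 − p) = B + (1 − B)p
- observed gap = (1 − B)(p₂ − p₁)

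**Step 3: illustration.** Assumed, not from the documents: true proportions of 10% v 30%, and B from 0 to 0.8. From the documents: 50 per arm and a 0.05 threshold, taken as two-sided.

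| B | Observed | Gap | Ratio | Power, normal approximation | Power, Fisher exact |
|---|---|---|---|---|---|
| 0 | 10% v 30% | 20 points | 3.0 | 71% | 64% |
| 0.2 | 28% v 44% | 16 points | 1.57 | 38% | 31% |
| 0.5 | 55% v 65% | 10 points | 1.18 | 17% | 13% |
| 0.8 | 82% v 86% | 4 points | 1.05 | 8% | not computed |

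Example at B = 0.5: 0.5 + 0.5 × 0.10 = 0.55; 0.5 + 0.5 × 0.30 = 0.65.

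**Step 4: a single overlapping term.** The same factor applies within one term. Section 3.0 cites sleep disorders in 30.8% of a hospitalized French cohort. If that share were present at entry and all logged, the factor would be 1 − 0.308 = 0.692, so the gap for sleep problems would shrink by about 31%. This trial excludes hospitalized cases, so the share may be lower. At 10% (assumed) the factor is 0.90.

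**Step 5: the first-10-subjects rule.** Take the rule to mean that all ten have an event. Averaging the arms in step 3, the chance is [1 − 0.8(1 − B)]¹⁰:
- B = 0: 0.2¹⁰, about 1 in 10 million
- B = 0.5: 0.6¹⁰ = 0.6%
- B = 0.8: 0.84¹⁰ = 17%

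Under these assumptions, old complaints alone can move the rule from practically unreachable to reachable.

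**The case against.** The strongest reply is that Section 19.1.2 already asks about events that occurred during the study and since the last visit. A complaint unchanged since before dosing did not occur in that interval, and the weekly calls give a chance to ask when it began. This stands as a partial safeguard. It is not a full one, because the judgement rests on recall with no baseline list, and no new-or-worse rule is written down.

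Four further points stand and limit the concern:
- No section turns the other-symptom entries in Appendix C into adverse events. Section 4.2 assigns that survey to the efficacy analysis.
- Dilution needs pooling or an overlapping term. Section 15.0 expects mainly gastrointestinal effects and also discusses bleeding. Neither is on the symptom list in Section 3.0, and joint pain does not dilute a diarrhea row. Sleep is the clear overlap, and Section 15.0 leaves insomnia out of monitoring. One version of the bleeding question in Section 15.0 asks about an increase, though the other does not.
- Adverse events are not a named endpoint, and no test specific to them is planned.
- The study schema figure is not shown, so a pre-dose Appendix C cannot be ruled out. It would help only in part: other symptoms are free text, and only fatigue is graded.

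**Conclusion.** The gap is real but moderate. As written, the plan cannot reliably separate old complaints from new or worsened ones in a sample that is symptomatic at entry. The likely result is reduced sensitivity of pooled any-event summaries and of terms that overlap with long covid, and old complaints can feed the stopping rule. The size is the factor (1 − B), given equal B in both arms and independence from true events. B is unknown, so the power figures are illustrative only.

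A reader might infer more, and the documents do not support it:
- **That every existing complaint automatically becomes an event.** The wording on events during the study points the other way.
- **That a true difference between arms is being hidden.** The documents give no event rates, and no masked difference is demonstrated.
- **That most subjects would be affected.** Five complaints at 10% to 30% each give 1 − 0.9⁵ = 41% to 1 − 0.7⁵ = 83%. That assumes independent symptoms and complete reporting. The cited prevalences of 21.7% to 34% come from hospitalized patients. These are upper bounds, not expectations.

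The primary feasibility endpoint is not affected. The change is worth making because it is nearly free and cannot be made good after dosing.

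**What to change.** 1. Add one checklist to Appendix B, completed before the first capsule. Include the four target symptoms, the other symptoms listed in Section 3.0, and the side effects named in Section 15.0, including bleeding. Grade each none, mild, moderate or severe over the past 14 days. A yes/no list would not do, because it cannot show worsening.
2. In Section 19.1.2, record the onset of each event. Count as treatment-emergent only symptoms absent at baseline or of higher grade than at baseline. Onset also identifies symptoms that begin between the survey and the first capsule. All events are still recorded and reported as now; the classification is added to them.
3. Tabulate treatment-emergent events by term and by arm, so that background complaints do not swamp terms that rarely pre-exist.
4. Have the sponsor state how the stopping rule in Section 15.0 relates to this classification. No rule is proposed here.

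Cost: a minute or two per subject on a survey already sent before capsules are mailed, a short addition to Section 19.1.2, and no extra contact.

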#### **6.2 Research Procedures**

For an overview of the study, please see figure 1 below.

1. Team members who email the study team at the address on the flyer will be sent an eligibility survey in REDCap to determine if study inclusion criteria are met.
2. Those who meet study inclusion criteria will then be sent the study consent form in REDCap, and encouraged to call or email the study team with questions.

3. If the patient expresses further interest in study participation, s/he will be consented via REDCap and then will be sent a link to the baseline survey in REDCap.
4. Upon consent, RC will assign ID# and enter the subject into REDCap (study data management system).
5. Subjects will be randomly assigned to receive 3 Omega-3 (EPA+DHA) mini-capsules twice daily (total of 2,100mg per day) for 12 weeks in the experimental intervention arm or three placebo mini-capsules twice daily for 12 weeks.
  - Study supplement or placebo are supplied at no cost to the subject and will be mailed to the subject's home.
  - Study subjects will receive two shipments over the course of study participation.
    - Package 1 upon enrollment
    - Package 2 at the end of week 4
  - Subjects will also receive, in these shipments, two spot blood sample tests for omega-3 levels, and directions indicating when to use the test kits.
6. All study subjects in each arm will be asked to give a spot sample (2 drops) of blood at baseline and again after 12 weeks (end of study participation). This will be done using OmegaQuant test kits that are mailed to the subject's home. The de-identified samples will be mailed by the subject in the provided envelope to OmegaQuant Lab, associated with University of South Dakota Medical Center, for analysis of omega-3 levels. These tests involve no cost to the subject. Subjects will be informed of their omega-3 level after results are returned from the lab and the subject's participation in the study is complete.
7. Monitoring of Subjects:
  - Subjects will be encouraged to call RC at any time with study questions. RC will also call each subject weekly to ensure procedures are being followed and answer any questions. The weekly "check-in call" will occur for 12 weeks.
  - Each subject will be checking their blood pressure. Subjects will report their blood pressure via REDCap in their bi-weekly survey. Reported adverse events will be documented.

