  - Subjects in both arms will be tracked for 3 months (12 weeks). An interim analysis will be done for a sub-sample (the first 20 subjects) after three weeks of participation to determine if any arm should be adjusted or terminated.
  - Participants will continue to receive standard of care and follow up for any routine conditions being managed at HackensackUMC.
8. The final study activity will include the 2nd spot blood sample and a short survey (survey link emailed to subject via REDCap) to collect feasibility and acceptability data. The survey will take about 10 minutes to complete.

9. Subjects will then be mailed a \$40 gift card for completing the study.

10. Subjects will be informed of their omega-3 level after results are returned from the lab and the subject's participation in the study is complete

Any subject missing both daily doses 3 times a week for 3 weeks in a row will be removed from the study for non-compliance, and asked to dispose of any unused study supplement/placebo. This will be documented in a dedicated RedCap survey for anyone who discontinues study participation, either for non-compliance or of their own will.

Any subject who has another covid-19 infection during study participation may continue on the study. The RC will inform the subject of this if/when any subject reports a new covid infection.

[figure not shown]

Figure 1: Study Schema

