## **8.0 Sharing of Results with Subjects**

Individual-level data (the results of both COVID-19 tests and the omega-3 levels from the blood draw if applicable) will be shared with participants. The major findings of the study and aggregate data, will be shared with participants after the study has concluded.

1) Unblinding will occur when a subject drops out of the study due to an adverse event. The subject will be informed of their study arm assignment via email so that they can better understand any possible adverse reaction to the study medication.

2) Subjects who complete the study will be unblinded and informed of their study arm assignment via email after the study team has seen their data (descriptive statistics generated by RedCap). This will be done within 4 weeks of each subject finishing the study.

The study coordinator will inform each subject when they finish study participation, to expect an email advising which study arm they were in.

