## 9.0 Study Timelines

Each subject will spend 12 weeks in the study.

It is anticipated that all subjects will be enrolled within a 6-month timeframe.

	Month 1	Month 2	Month 3	Month 4	Month 5	Month 6	Month 7	Month 8	Month 9	Month 10	Month 11	Month 12
IRB approvals & startup	X	X	X									
Enrollment				X	X	X	X	X				
Subjects on study (12 weeks)				X	X	X	X	X	X	X	X	X
Interim analysis at 3 weeks					X							
Final data analysis										X	X	X

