Experience with the approved preparations and clinical studies is that adverse events are relatively minor in nature and severity, and are primarily related to gastro-intestinal effects.

During the study the subject will take a health survey bi-weekly and will be asked to report any health concerns to the PI. Reported adverse events will be documented. Additionally, the Research Coordinator (RC) will also call each subject weekly for the

duration of the study (total of 12 weeks) to ensure procedures are being followed, answer any questions, and refer any health issues to the PI.

- If any individual subject experiences an adverse event (AE), the PI will determine whether to stop study participation for that individual.
- If the first 10 subjects experience an AE, the study will stop. This decision will be made under the direction of the IRB in consultation with the DSMB as described below in section 19.2 Data Safety Monitoring.

Risks to subjects from Soybean Oil Placebo:

The placebo is made from soybean oil. There is an allergy risk associated with ingesting soy. The study eligibility criteria excludes any person with a soy allergy.

Risks Associated with Washout:

There are no known risks associated with washout from omega-3 supplement or the soybean oil placebo.

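### No visible scheduled contact falls in the 30-day adverse event window after last dose, and completers may be told their arm before that window closes

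*Combined protocol and SAP*

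**What the plan says.** Section 19.1.2 sets the recording window: "AE will be reported and recorded from the time of the first dose of study drug through 30 days after the last dose". It repeats the duty as a minimum: "AE monitoring should be continued for at least 30 days following the last dose of study supplement". It also describes how events are to be found: "The Investigator should ask the patient non-leading questions to determine if any AEs have occurred during the study, since the last visit". Events that subjects volunteer are accepted as well.

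The contact schedule is built on 12 weeks. Section 9.0 states: "Each subject will spend 12 weeks in the study". Section 6.2 says the "RC will also call each subject weekly", for 12 weeks, and Section 15.0 describes these calls as lasting for the "duration of the study (total of 12 weeks) to ensure procedures are being followed". Section 1.0 places the bi-weekly surveys within the same 12 weeks. Section 6.2 makes the second blood spot and the feasibility survey the last study activity. After that, Section 19.3 has one phone survey at 6 months after last dose, with no listed content. Section 19.0 lets a subject telephone the principal investigator at any time.

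On disclosure, Section 8.0 item 2 has completers emailed their arm once the team has seen their data, and adds: "This will be done within 4 weeks of each subject finishing the study". Item 1 has subjects who drop out because of an adverse event told their arm at dropout.

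**The concern.** The plan states an active collection rule for the 30 days after last dose but shows no step that carries it out. The trial is run remotely, so no clinic visit fills the gap. The bleeding question belongs to the weekly call (monitoring summary, Section 15.0), and the bi-weekly survey in Appendix C has no general adverse event question beyond symptoms, blood pressure and an optional comment. When the calls stop, routine questioning stops. The form for early discontinuers in Appendix D asks about stopping, pill count and discarding pills, and nothing about adverse events.

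A summary over the whole recording window would therefore combine prompted reports on treatment with volunteered reports afterwards. Some of the latter could come from subjects who have already been told their arm. The lack of contact is the same in both arms, but knowledge of the arm can shift reporting differently in each. What is at stake is the post-dose safety record that this proof-of-concept study passes to the larger trial, together with avoidable departures from its own rule.

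**Working it through.** The plan gives no calculated figure to reproduce; the check is calendar arithmetic.

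**Inputs.** Treatment and time on study: 12 weeks (Sections 6.2 and 9.0). Recording window after last dose: 30 days (Section 19.1.2). Latest arm email for completers: 4 weeks after finishing (Section 8.0). Later call: 6 months after last dose (Section 19.3), taken here as about 182 days.

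**Uncovered time.**
- Last dose: 12 × 7 = day 84.
- Window closes: 84 + 30 = day 114.
- Share of the window with no scheduled contact: 30 / 114 = 26.3%.
- The 6-month call: 84 + 182 = day 266, which is 266 − 114 = 152 days after the window closes.

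**Disclosure against the window.** Let L be the number of days from last dose to finishing. The latest on-schedule email is then L + 28 days after last dose.
- L = 0: day 28 after last dose (84 + 28 = study day 112), 2 days before the window closes.
- L = 2: 2 + 28 = day 30, exactly at the close.
- L = 3: 3 + 28 = day 31, so the deadline now falls after the window.

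Overlap is therefore certain for an on-schedule email only if finishing falls within about 2 days of last dose. With a longer lag it is still possible, because Section 8.0 sets a latest date and no earliest date.

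**Days of the window left after disclosure**, for an email sent u days after last dose (30 − u): u = 0 gives 30 days, u = 14 gives 16, u = 28 gives 2.

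**Illustration of under-counting.** Assume a constant event rate over the 114 days, full capture on treatment, and a fraction f of post-dose events reported spontaneously. The share of all events missed is 30 × (1 − f) / 114:

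| f | Share missed |
|---|---|
| 0% | 26.3% |
| 25% | 19.7% |
| 50% | 13.2% |
| 75% | 6.6% |
| 100% | 0% |

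The documents give neither an event rate nor f, so this shows a range under assumptions and is not an estimate.

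**The case against.** The strongest reply is that Section 19.1.2 already obliges the investigator to ask and to keep monitoring, subjects can phone at any time, and a missing calendar entry does not prove that the rule cannot be met. That is fair. The finding is that no visible step implements the rule, not that compliance is impossible. Absence also cannot be fully checked: the Figure 1 schema is not shown and the consent pages are not available, and either might describe a post-dose contact.

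It can also be said that little is lost. Section 15.0 describes expected events as relatively minor and mainly gastro-intestinal, with no known risk from washout. Section 17.1 names no specific adverse event test and says the study is not powered. The on-treatment summary is untouched, and the feasibility survey asks about new diagnoses since starting. All of this stands and limits the importance of the point. The conflict between the rule and the schedule remains.

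A reader might infer three stronger claims that the documents do not support:
- That all scheduled contact ends at week 12. Section 19.3 schedules the 6-month call; the problem is that it comes long after the window and is not said to collect adverse events.
- That 26% of events will be lost. That figure is calendar time only.
- That safety reporting as a whole is unblinded. Only reports made after a subject's own disclosure are affected, and subjects still on study in weeks 1 to 12 have not been told.

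**Conclusion.** The point holds as a mismatch between the adverse event rule and the visible contact schedule, made worse by the timing of disclosure. Thirty of 114 window days (26.3%) have no scheduled questioning, taking last dose at day 84. Completers can be told their arm before the window closes, and always will be if the email is on schedule and finishing falls within about 2 days of last dose. Under-counting and arm-aware reporting are risks whose size cannot be derived from the documents.

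The clearest case of disclosure before follow-up ends is the subject who drops out because of an adverse event. Section 8.0 has that subject told at dropout, while Section 19.1.2 still asks for later assessment of the event's relationship to treatment and its outcome.

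The sample size, the week-12 comparison and the feasibility result are unaffected. The point is worth correcting because the remedy is cheap, not because the trial fails without it.

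**What to change.** 1. Schedule one short REDCap form or coordinator call at day 30 after last dose. Use the same non-leading adverse event and bleeding questions in both arms, and include subjects who stop early, timed from their own last dose.
2. Amend Section 8.0 item 2 so that a completer's arm email goes out once that contact is recorded. For non-responders, send it once a fixed date after day 30, set in advance, has passed, so that nobody is left uninformed.
3. Leave Section 8.0 item 1 as it is. Record the date of every disclosure and flag adverse event data collected after it as unblinded.
4. Reconcile Sections 6.2, 8.0, 15.0, 19.1.2 and 19.3, stating who collects events between last dose and day 30 and whether the 6-month call asks about them.

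The cost is at most 120 short forms or calls by existing staff, plus a protocol amendment. Completers' emails move later: by about 2 days (30 − 28) where the email would have gone on day 28 after last dose, and by up to about 30 days where it would have gone at once.
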